### **12.2.2. Serious Adverse Events**

A serious adverse event based on ICH and EU Guidelines on Pharmacovigilance for Medicinal Products for Human Use is any untoward medical occurrence that at any dose:

- Results in death
- Is life-threatening  
(The subject was at risk of death at the time of the event. It does not refer to an event that hypothetically might have caused death if it were more severe.)
- Requires inpatient hospitalization or prolongation of existing hospitalization

- Results in persistent or significant disability/incapacity
- Is a congenital anomaly/birth defect
- Is a suspected transmission of any infectious agent via a medicinal product
- Is Medically Important\*

\*Medical and scientific judgment should be exercised in deciding whether expedited reporting is also appropriate in other situations, such as important medical events that may not be immediately life threatening or result in death or hospitalization but may jeopardize the subject or may require intervention to prevent one of the other outcomes listed in the definition above. These should usually be considered serious.

If a serious and unexpected adverse event occurs for which there is evidence suggesting a causal relationship between the study drugs and the event (eg, death from anaphylaxis), then the event must be reported as a serious and unexpected suspected adverse reaction even if it is a component of the study endpoint (eg, all-cause mortality).

All serious adverse events occurring during the study must be reported to the appropriate sponsor contact person by study-site personnel within 24 hours of their knowledge of the event.

Information regarding serious adverse events will be transmitted to the sponsor using the Serious Adverse Event Form, which must be completed and signed by a physician from the study site, and transmitted to the sponsor within 24 hours. The initial and follow-up reports of a serious adverse event should be made by facsimile (fax).

All serious adverse events that have not resolved by the end of the study, or that have not resolved upon discontinuation of the subject's participation in the study, must be followed until any of the following occurs:

- The event resolves
- The event stabilizes
- The event returns to baseline, if a baseline value/status is available
- The event can be attributed to agents other than the study drug or to factors unrelated to study conduct
- It becomes unlikely that any additional information can be obtained (subject or health care practitioner refusal to provide additional information, lost to follow-up after demonstration of due diligence with follow-up efforts)

Suspected transmission of an infectious agent by a medicinal product will be reported as a serious adverse event. Any event requiring hospitalization (or prolongation of hospitalization) that occurs during the course of a subject's participation in a study must be reported as a serious adverse event, except hospitalizations for the following:

- Administration of study drugs
- Hospitalizations not intended to treat an acute illness or adverse event (eg, social reasons such as pending placement in long-term care facility)

- Surgery or procedure planned before entry into the study (must be documented in the eCRF). Note: Hospitalizations that were planned before the signing of the ICF, and where the underlying condition for which the hospitalization was planned has not worsened, will not be considered serious adverse events. Any adverse event that results in a prolongation of the originally planned hospitalization is to be reported as a new serious adverse event.
- For convenience the investigator may choose to hospitalize the subject for the duration of the treatment period.

### **12.2.3. Disease Progression**

Disease progression should not be recorded as an adverse event or serious adverse event term; instead, signs and symptoms of clinical sequelae resulting from disease progression/lack of efficacy will be reported if they fulfill the serious adverse event definition (refer to Section 12.1.1, Adverse Event Definitions and Classifications).

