#### 9.5. Safety Evaluations

The evaluation period for safety will start from the time a signed consent/assent is provided. Toxicity/safety will be determined using National Cancer Institute common terminology criteria for adverse events (NCI-CTCAE) version 4.0.

The primary expected toxicity of cytarabine is severe myelosuppression. In addition rare cases of hypersensitivity and anaphylaxis have been reported after cytarabine dosing as well as “sudden respiratory arrest syndrome” occurring 6 to 12 hours after dosing and tumor lysis syndrome.

In addition to myelosuppression, administration of DACOGEN can cause peripheral edema, pallor, cardiac murmur and hypotension. Fever, fatigue, headache, lethargy and other CNS symptoms may occur. Cough, dyspnea, pneumonia and pharyngitis may be seen as well as mucositis and other side effects associated with myelosuppression and cellular cytotoxicity.

For the purposes of DLT evaluation, Cycle 1 will last until the start of Cycle 2, unless there is no recovery from toxicity within the specified time.

During the conduct of Phase 1 the SET will evaluate the tolerability of the combination until such times as a MTD for cytarabine can be agreed upon. Details regarding the SET are provided in Section 11.9.

During Phase 1, blood counts are to be monitored, but hematological parameters are not used to determine the MTD (ie, low blood counts per se are not considered to be dose-limiting toxicities or serious adverse events) because peripheral blood counts and bone marrow function are compromised in patients with relapsed leukemia. Hematological toxicity will only be assessed in responding patients who have grade 4 neutropenia ( $<0.5 \times 10^9/L$ ) or grade 4 thrombocytopenia ( $<25 \times 10^9/L$ ) due to a hypoplastic marrow at Day 42, in the absence of leukaemia.

During Phase 2 only myelosuppression events that are considered life threatening or result in an admission to hospital would be considered as serious adverse events.

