Safety will be measured by adverse events, laboratory test results, vital sign measurements, physical examination findings, and assessment of performance status. Any clinically relevant changes occurring during the study must be recorded on the Adverse Event section of the eCRF. Any clinically significant abnormalities persisting at the end of the study/early withdrawal will be followed by the investigator until resolution or until a clinically stable endpoint is reached. The study will include the following evaluations of safety and tolerability according to the time points provided in the Time and Events Schedule.

Any of the safety monitoring assessments may be performed more frequently, and adverse events should be evaluated by the investigator according to standard practice, and if clinically indicated.

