## Adverse Events

Adverse events (with the exception of disease progression) will be reported by the subject (or, when appropriate, by a caregiver, surrogate, or the subject's legally acceptable representative) or by the medical staff from the time of the signed and dated ICF until 30 days following the last dose of any study drug. Adverse events will be followed by the investigator as specified in Section 12, Adverse Event Reporting.

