**12.1.3. Severity Criteria**

An assessment of severity grade will be made using the National Cancer Institute Common Terminology Criteria for Adverse Events (NCI-CTCAE) version 4.0. Special Reporting Situations

Safety events of interest on a sponsor study drug that may require expedited reporting and/or safety evaluation include, but are not limited to:

- Overdose of a sponsor study drug
- Suspected abuse/misuse of a sponsor study drug
- Inadvertent or accidental exposure to a sponsor study drug
- Any failure of expected pharmacologic action (ie, lack of effect) of a sponsor study drug
- Unexpected therapeutic or clinical benefit from use of a sponsor study drug
- Medication error involving a sponsor product (with or without subject/patient exposure to the sponsor study drug, eg, name confusion)

Special reporting situations should be recorded in the eCRF. Any special reporting situation that meets the criteria of a serious adverse event should be recorded on the serious adverse event page of the eCRF.

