**12.2. Procedures****12.2.1. All Adverse Events**

All adverse events and special reporting situations, whether serious or non-serious, will be reported from the time a signed and dated ICF is obtained until 30 days after the last dose of study drug. Serious adverse events, including those spontaneously reported to the investigator

within 30 days after the last dose of study drug, must be reported using the Serious Adverse Event Form. The sponsor will evaluate any safety information that is spontaneously reported by an investigator beyond the time frame specified in the protocol.

All events that meet the definition of a serious adverse event will be reported as serious adverse events, regardless of whether they are protocol-specific assessments.

All adverse events, regardless of seriousness, severity, or presumed relationship to study drug, must be recorded using medical terminology in the source document and the eCRF. Whenever possible, diagnoses should be given when signs and symptoms are due to a common etiology (eg, cough, runny nose, sneezing, sore throat, and head congestion should be reported as "upper respiratory infection"). Investigators must record in the eCRF their opinion concerning the relationship of the adverse event to study therapy. All measures required for adverse event management must be recorded in the source document and reported according to sponsor instructions.

The sponsor assumes responsibility for appropriate reporting of adverse events to the regulatory authorities. The sponsor will also report to the investigator (and the head of the investigational institute where required) all serious adverse events that are unlisted (unexpected) and associated with the use of the study drug. The investigator (or sponsor where required) must report these events to the appropriate Independent Ethics Committee/Institutional Review Board (IEC/IRB) that approved the protocol unless otherwise required and documented by the IEC/IRB.

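### Section 12.2.3 ties reporting of progression-related signs and symptoms to seriousness, which conflicts with Section 12.2.1 and leaves room to omit non-serious clinical events blamed on leukemia

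*Combined protocol and SAP*

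**What the plan says.** Section 12.2.3 has two parts. The first bars disease progression as an adverse event or serious adverse event term. The second says what happens in its place: "signs and symptoms of clinical sequelae resulting from disease progression/lack of efficacy will be reported if they fulfill the serious adverse event definition". It does not mention signs and symptoms that fall short of the serious definition.

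Section 12.2.1 sets the general duty in two sentences. On reporting: "All adverse events and special reporting situations, whether serious or non-serious, will be reported from the time a signed and dated ICF is obtained". On recording: "All adverse events, regardless of seriousness, severity, or presumed relationship to study drug, must be recorded", in both the source document and the eCRF.

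Section 9.5 has two further rules. Its Adverse Events paragraph begins "Adverse events (with the exception of disease progression) will be reported by the subject", so the exception covers progression itself and does not mention its consequences. Earlier in the same section: "Any clinically relevant changes occurring during the study must be recorded on the Adverse Event section of the eCRF". Neither rule has a seriousness filter for sequelae.

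Section 11.8 builds the adverse event summaries from reported events with onset during treatment. No section states an order of precedence between 12.2.1 and 12.2.3.

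**The concern.** Barring the term itself is ordinary practice and is not at issue. The difficulty is that, once the investigator puts a sign or symptom down to progression or lack of efficacy, 12.2.3 makes its reporting depend on seriousness.

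That attribution is hard to make here. Every child enters with active leukemia, and the study drugs are myelosuppressive. Section 9.5 acknowledges the overlap when it explains why low counts alone are not dose-limiting: "peripheral blood counts and bone marrow function are compromised in patients with relapsed leukemia". Section 9.2.1 lets progression rest on the investigator's clinical judgment, and lack of efficacy is not defined for this purpose. Under the restrictive reading, an uncertain judgment about cause decides whether a non-serious event enters the database at all.

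The safety profile is a secondary endpoint with no control arm against which selective recording might balance out, and Section 3.1.2 provides no independent data monitoring committee. Sites that follow 12.2.1 and sites that follow 12.2.3 would contribute incidences that are not comparable, and the tables would not show it.

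**Working it through.** The plan states no figure on this point, so the check is textual.

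**1. Do the two sections govern the same act?**

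| | 12.2.1 | 12.2.3 |
|---|---|---|
| Act | reported, and recorded in source and eCRF | reported |
| Events | all adverse events | signs and symptoms from progression or lack of efficacy |
| Seriousness | irrelevant | a condition |
| Presumed cause | irrelevant | triggers the rule |

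Section 12.2.1 uses the verb *reported* for non-serious events too. The two sections therefore cannot be separated by saying that one concerns the eCRF and the other only expedited reporting.

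**2. Which readings of 12.2.3 are open?**

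- *Reading A:* it covers only what goes on the Serious Adverse Event Form, and the 12.2.1 duty continues. Its place after the serious adverse event section supports this.
- *Reading B:* it replaces ordinary handling for these events. Its first part concerns both adverse event and serious adverse event terms, and its second part is offered as the substitute. Under Reading A it would add little, because 12.2.1 already requires any event meeting the serious definition to be reported as serious.

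Both are reasonable, and the text does not choose.

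**3. What happens under Reading B?** The non-serious event is not reported. Section 11.8 summarizes reported events, so it is absent from the incidence tables.

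**4. Which events are exposed?**

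- Scheduled laboratory abnormalities: not exposed. Section 11.8 summarizes graded laboratory parameters and gives shift tables to worst grade from laboratory data.
- Life-threatening or medically important events, and those requiring hospitalization for an acute illness: not exposed, because they meet the serious definition in 12.1.1.
- Febrile neutropenia and suspected sepsis: generally not exposed, because Section 8 has these patients hospitalized. Section 12.2.2 does exempt admission for convenience during treatment, so inpatient status alone does not make an event serious.
- Non-serious clinical (non-laboratory) events blamed on leukemia: exposed.

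**5. Does this reach dose decisions?** It depends on which DLT wording applies.

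- Section 9.2.2, Grade 3 or higher: the event must be at least possibly related to study drug, and several likely disease-related events are excluded by name. An event blamed on leukemia would generally not count even if recorded, unless its attribution were revised.
- Section 9.2.2, Grade 2 criterion (more than 7 days and intolerable): no attribution condition.
- Section 3.1.1 and the Synopsis: no attribution condition at either grade.

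An unrecorded non-serious event could therefore matter to the SET mainly under the last two.

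**6. Can the loss be sized?** No. The documents give neither a rate of non-serious progression-related events nor the share of sites that would adopt Reading B. The only available scale is the weight of one child. With the 17 subjects Section 11.2 estimates for Phase 2, each subject whose only occurrence of an event goes unreported lowers that event's incidence by 1/17 = 5.9 percentage points. This is a unit of scale and does not estimate the loss.

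**The case against.** The best defense is that 12.2.3 never says *only*. It is silent on non-serious sequelae, and silence need not cancel the explicit duties in 12.2.1 and 9.5. Footnote i of the Time and Events Schedule also has signs and symptoms of disease assessed at each treatment visit. An event is lost only if a site lets one clause override all of these. This stands as a limit: the documents establish an unreconciled conflict, and they do not establish that events will go unrecorded. It does not remove the conflict, because Reading B is one a careful site could adopt.

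Four stronger inferences are tempting and are not supported:

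- *That Grade 3-4 events in general would vanish.* Laboratory toxicities and serious events reach the safety profile by other routes (step 4).
- *That the SET would never see such events.* Section 11.9 gives it the Phase 1 safety data without limiting it to adverse event listings. The supportable statement is that an event never entered may not reach it.
- *That the understatement can be quantified from the plan's 20% and 35% response rates.* Section 11.4 uses these as benchmarks for clinical interest. Any incidence built on them would also need event and misattribution rates that the documents do not contain.
- *That 12.1.3 adds a third conflicting rule* by listing "Any failure of expected pharmacologic action (ie, lack of effect) of a sponsor study drug" among special reporting situations. That list concerns safety events of interest on the study drug and does not govern signs and symptoms of progression. Carving leukemia non-response out of it would remove recording, which is the opposite of what is needed here.

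**Conclusion.** The point holds in a limited form. Sections 12.2.1 and 12.2.3 give different reporting conditions for the same events, Section 9.5 does not support a carve-out for sequelae, and nothing settles precedence. Non-serious clinical events attributed to leukemia can therefore be omitted by a site acting reasonably, and would then be missing from the adverse event summaries. The possible effect on dose decisions is secondary and depends on which of the inconsistent DLT definitions is applied.

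This rests on one assumption: that at least one site reads 12.2.3 as overriding the general rule. If every site follows 12.2.1, nothing is lost. The direction of any bias is toward understating adverse event incidence; its size cannot be derived from the documents. No endpoint definition or stated estimate is shown to be wrong. The wording is still worth correcting, because the correction is cheap and events not recorded at the time may not be recoverable later.

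**What to change.** In Section 12.2.3, keep the statement that disease progression is not entered as an adverse event or serious adverse event term. Replace the conditional clause with text to this effect:

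> Signs and symptoms thought to result from disease progression or lack of efficacy are recorded as adverse events, with CTCAE grade and investigator attribution, as Section 12.2.1 requires, whatever their seriousness. Those that meet the serious definition are also reported as serious adverse events.

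Repeat the rule in the eCRF completion guidelines so that all sites apply it alike. Leave the special reporting list in 12.1.3 unchanged. Separately, the attribution wording of the DLT definitions in the Synopsis, Section 3.1.1 and Section 9.2.2 needs to be reconciled by the sponsor; which version applies is not a matter for this point.

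The cost is one reworded sentence in an amendment and a matching line of site guidance. Sites already following 12.2.1 take on no new duty. Others will record somewhat more non-serious events, and stated adverse event rates may be slightly higher.

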### **12.2.4. Pregnancy**

All initial reports of pregnancy must be reported to the sponsor by the study-site personnel within 24 hours of their knowledge of the event using the appropriate pregnancy notification form. Abnormal pregnancy outcomes (eg, spontaneous abortion, stillbirth, and congenital anomaly) are considered serious adverse events and must be reported using the Serious Adverse Event Form. Any subject who becomes pregnant during the study must be promptly withdrawn from the study and discontinue further study treatment.

Because the study drug may have an effect on sperm, pregnancies in partners of male subjects included in the study will be reported by the study-site personnel within 24 hours of their knowledge of the event, using the appropriate pregnancy notification form.

Follow-up information regarding the outcome of the pregnancy and any postnatal sequelae in the infant will be required.

### **12.3. Contacting Sponsor Regarding Safety**

The names (and corresponding telephone numbers) of the individuals who should be contacted regarding safety issues or questions regarding the study are listed on the Contact Information page(s), which will be provided as a separate document.

## **13. PRODUCT QUALITY COMPLAINT HANDLING**

A product quality complaint (PQC) is defined as any suspicion of a product defect related to manufacturing, labeling, or packaging, ie, any dissatisfaction relative to the identity, quality, durability, or reliability of a product, including its labeling or package integrity. A PQC may have an impact on the safety and efficacy of the product. Timely, accurate, and complete reporting and analysis of PQC information from studies are crucial for the protection of subjects, investigators, and the sponsor, and are mandated by regulatory agencies worldwide. The sponsor has established procedures in conformity with regulatory requirements worldwide to ensure appropriate reporting of PQC information; all studies conducted by the sponsor or its affiliates will be conducted in accordance with those procedures.

### **13.1. Procedures**

All initial PQCs must be reported to the sponsor by the study-site personnel within 24 hours after being made aware of the event.

If the defect is combined with a serious adverse event, the study-site personnel must report the PQC to the sponsor according to the serious adverse event reporting timelines (refer to Section 12.2.2, Serious Adverse Events). A sample of the suspected product should be maintained for further investigation if requested by the sponsor.

### **13.2. Contacting Sponsor Regarding Product Quality**

The names (and corresponding telephone numbers) of the individuals who should be contacted regarding product quality issues are listed on the Contact Information page(s), which will be provided as a separate document.

## **14. STUDY DRUG INFORMATION**

### **14.1. Physical Description of Study Drug(s)**

The DACOGEN supplied for this study is the commercially approved product that will be relabeled in local languages as “Clinical Supply Only”. DACOGEN (decitabine) for Injection is a white to almost white sterile lyophilized powder supplied in a single-use 20 ml vial containing 50 mg decitabine. It will be manufactured and provided under the responsibility of the sponsor. Refer to the Investigator's Brochure for a list of excipients.

Cytarabine for this study will be the commercially approved product and locally sourced by each investigator site. Refer to the SmPC of cytarabine for product details.

